7.2 Patient Disposition

Patient disposition data will be presented overall.

The number of enrolled patients will be presented overall. The number (%) of patients included in each other analysis set (Safety set, FAS and PPS) will be presented overall.

The number (%) of patients by centre will be presented overall, for FAS and PPS.

The number (%) of patients per visit as considered in the analysis (i.e., after remapping of the premature discontinuation visit) will be described overall for FAS and PPS.

A listing of patients with information on analysis sets and studied eye will be produced for the enrolled patients and a listing of actual visits and visits as considered in the analysis (see Section 5.1) will be produced for the FAS.

The number (%) of patients who prematurely discontinued the study and the primary reason for discontinuation will be presented overall for the Safety Set and FAS. The number (%) of patients who prematurely discontinued the IMD and the primary reason for discontinuation will be presented overall for the Safety Set and FAS. A listing will be produced on the Safety Set presenting the patients who prematurely discontinued the study or the IMD with the detailed reason for discontinuation.

A listing of patients excluded from FAS, PPS or Safety set, presenting the reason for exclusion, will be produced on the enrolled patients.

CCI

7.3 Protocol Deviations

The list of potential protocol deviations will be pre-defined in separate document.

Prior to data lock for analysis, a meeting will be held to review protocol deviation classification, and to agree on the analysis sets.

The number (%) of patients with at least one major deviation, the number (%) of patients with only minor deviations (without major deviations) and the number (%) of patients with minor deviations (including those with major deviations) will be presented overall for the FAS. The deviations will also be described for FAS and a listing with all minor/major deviations will be provided.

7.4 Demographics and Baseline Characteristics

The following demographic will be summarized using descriptive statistics and presented overall using the Safety Set, FAS and PPS:

- Demographics:
 - Age (years) as continuous and in three classes (< 65 / ≥ 65 and <85 / ≥85 years old),
 - Gender (Male / Female),
 - Gender by age class.

The following baseline characteristics will be summarized using descriptive statistics and presented overall using the FAS and PPS:

- Contact Lens History:
 - Contact lens type (Soft / Rigid gas permeable),
 - If soft contact lens type, replacement modality (Daily / Weekly / Bi-Weekly / Monthly / Every 3 months / Every 6 months / Yearly),
 - If not daily contact lens, contact lens solution type (Preserved / Not preserved),
 - History of contact lens intolerance (Yes / No).
- DED History:
 - Time since DED diagnosis (months) in the studied and the contralateral eyes.

Data regarding contraception status, effective method of contraception and pregnancy test results (for women) will be presented in an individual data listing CCI

Baseline values of the performance and safety endpoints will be provided in statistical tables with assessments at D15 and D36 (see Sections 7.8 and 7.10).

7.5 Medical History

Diagnosis (for medical history) and surgical procedures (for surgical history) will be coded using the Medical Dictionary for Regulatory Activities (MedDRA) version 26.1, English or higher.

Number (%) of patients will be presented by SOC and PT using the FAS and PPS:

- Medical history:
 - Ocular medical history (included DED),
 - Systemic medical history.
- Surgical history:
 - Ocular surgical history,
 - Systemic surgical history.

7.6 Prior and Concomitant Medications

All previous and concomitant ocular and non-ocular treatments will be coded using World Health Organization-Drug Dictionary (WHO-DD) version Format C3, September 1, 2022 or higher.

Treatments will be summarised according to the Anatomical therapeutic chemical (ATC) class (level 2 and level 4) of the WHO-DD dictionary.

A previous treatment will be defined as a treatment stopped prior to (or the same day as) the first instillation of the IMD.

A concomitant treatment will be defined as a treatment i) started after (or the same day as) the first instillation of the IMD, ii) started prior to and continued after the first instillation of the IMD. If the classification is not possible due to partial start/end date(s) of treatment, the treatment will be considered as concomitant.

Number (%) of patients will be presented by ATC4 and ATC2 using the FAS and the PPS:

- Ocular treatments
 - Previous ocular treatments,
 - Concomitant ocular treatments.
- Non-ocular treatments
 - Previous non-ocular treatments,
 - Concomitant non-ocular treatments.

7.7 Treatment Exposure and Compliance

The following data on the use of the IMD will be summarized using descriptive statistics overall using the FAS and PPS:

- Treated eye (Right eye / Left eye/ Both eyes),
- Duration of exposure (days),
- Mean daily dose regimen (less than 3 / 3 instillations/day / 4 instillations/day / 5 instillations/day / 6 instillations/day and more than 6) at D15 and D36,
- Total number of days with study treatment (between D1 and D15, between D16 and D36 and between D1 and D36) for the studied eye and the contralateral eye separately.

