7.1 ANALYSIS POPULATION AND PROCEDURES

The following analysis sets will be considered:

- **Safety set:**

All enrolled patients, having received at least one instillation of IMD.

The safety set will be the primary population for safety analysis.

- **Full-Analysis Set (FAS):**

All enrolled patients having received at least one instillation of IMD.

The FAS will be the primary population for performance analysis.

- **Per protocol (PP) set:**

Subset of the FAS including patients without any major CIP violations likely to seriously affect the primary outcome of the study.

Deviations from the CIP will be defined and assessed as “minor” or “major” in cooperation with the sponsor during a data review meeting before the database lock.

The PP set will be considered as secondary population and will be used for sensitivity analyses of the primary and secondary endpoints.

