7.2 STATISTICAL ANALYSIS

Quantitative variables (Continuous data) will be summarized in summary tables indicating the number of non-missing observations (n), mean, SD, median, lower quartile (Q1), upper quartile (Q3), minimum and maximum, and 95% Confidence Interval (CI) of the mean/median.

Qualitative variables (Categorical data) will be summarized in summary tables indicating the number of non-missing observations (n), count and percentage of each modality, and 95% CI.

Baseline is defined as the assessment at D1 visit before the first IMD. Missing value at inclusion visit will not be replaced.

For endpoints defined as change from baseline (D1), the descriptive statistic by visit and the change from baseline will be presented.

Parameters recorded for both eyes will be described separately for the studied eye and for the contralateral eye.

CCI

Disposition, demographics, baseline characteristics including contact lens history, medical/surgical history, previous and concomitant treatments, and exposure will be summarized for the FAS and PP.

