5.3 Other Data Analyses Considerations

Strata and Covariates

Not Applicable.

Multiple Comparisons and Multiplicity

There is a single primary performance endpoint in the study (change from baseline to D36 in the CLDEQ-8 total score). Other performance measures are defined as of secondary importance. Thus comparison will be performed at a two-sided significance level of CCI; no adjustment of the type I error rate will be made.

6 Analysis Sets

Analysis sets to be used for the analyses are described in the table below.

Table 1: Analysis Sets

Analysis Set	Description
Enrolled set	All patients who have signed the informed consent form and for whom the inclusion visit has been recorded in the eCRF.
Safety set	All enrolled patients, having received at least one instillation of IMD. The safety set will be the primary population for the safety analysis.
Full-Analysis set (FAS)	All enrolled and included (i.e., started the treatment period) patients, having received at least one instillation of IMD and with at least one baseline and one post-baseline performance assessment. The FAS will be the primary population for the performance analysis.

Analysis Set	Description
Per-protocol set (PPS)	
Subset of the FAS including patients without any major clinical investigation plan (CIP) violations likely to seriously affect the primary outcome of the study.
 
Deviations from CIP will be detailed in a separate document and assessed as “minor” or “major” during data review meeting before the database lock.
 
The PPS will be considered as a secondary population and will be used for sensitivity analyses of the primary and secondary endpoints.

7 Methods of Analysis

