7.10 Safety Analyses

All safety analyses will be performed using descriptive statistics overall using the Safety set, unless otherwise specified.

CCI

Published date: 29Mar2023

Effective date: 12Apr2023

CONFIDENTIAL

Page 20 of 24

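### Exposure and concomitant treatments are tabulated on the SAP's narrowed FAS and PPS, but adverse events on the Safety set, so the two can describe different patients

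*SAP*

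**What the plan says.** **Protocol.** Section 7.1 defines the Safety set as "All enrolled patients, having received at least one instillation of IMD" and gives the FAS the same requirement. Section 7.2 then says that "previous and concomitant treatments, and exposure will be summarized for the FAS and PP".

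**SAP analysis sets (section 6).** The Safety set still needs only one instillation. The FAS is now limited to included patients "having received at least one instillation of IMD and with at least one baseline and one post-baseline performance assessment".

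**SAP tables.**
- Section 7.7, on use of the device: "The following data on the use of the IMD will be summarized using descriptive statistics overall using the FAS and PPS".
- Section 7.6, on previous and concomitant treatments: "Number (%) of patients will be presented by ATC4 and ATC2 using the FAS and the PPS".
- Section 7.10, on safety: "All safety analyses will be performed using descriptive statistics overall using the Safety set, unless otherwise specified".

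SAP section 9 lists the more specific FAS definition among the changes from the protocol. It does not mention what that does to the exposure and treatment tables.

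**The concern.** An exposure table tells the reader how much treatment lies behind the adverse event percentages, and a concomitant treatment table shows what else those patients were taking. Both serve that purpose only if they cover the same patients as the adverse event tables. The protocol's definitions ensured this. The SAP's do not, because it changed the definition of one set without reviewing every table assigned to it.

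The SAP does treat the two sets as different elsewhere. Demographics (7.4) are shown on the Safety set as well as the FAS and PPS, and premature discontinuations (7.2) on the Safety set and FAS. The treatment and exposure tables were not brought into line.

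At stake is the description of exposure in the treated population. A patient followed too briefly to give a performance assessment is also likely to have short recorded use, so omission would tend to push the displayed mean upwards.

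**Working it through.** The documents give no figure to reproduce: the sample size is blacked out and there is no formal calculation. The check is one of set logic, followed by an illustration of size.

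**1. Who falls between the sets**

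| | Safety set | FAS | Safety set minus FAS |
|---|---|---|---|
| Protocol 7.1 | at least one instillation | at least one instillation | empty |
| SAP section 6 | at least one instillation | at least one instillation, plus a baseline and a post-baseline performance assessment | dosed patients lacking either assessment |

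A baseline is almost always present, because CLDEQ-8 and OSDI scores are inclusion criteria (protocol 6.3.1). In practice the gap is dosed patients with no post-baseline performance assessment.

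**2. Whether the plan foresees such patients**

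- Protocol 6.1.6.6 allows discontinuation by phone in exceptional circumstances. The call collects compliance, adverse events, device deficiencies and treatment changes, but none of the performance measures. The on-site safety follow-up listed after it includes none either.
- Protocol 6.3.3 provides for patients lost to follow-up.
- Protocol 6.1.6.4 asks for a premature discontinuation visit only where possible.
- SAP 4.5 allows for about 10% drop-out or non-evaluable patients, and defines evaluable as one dose plus one performance evaluation.

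**3. Where they appear.** They are in the numerators and denominators of the SAP 7.10.1 tables. They are in no summary of duration of exposure, daily regimen, days treated (7.7), or previous and concomitant treatments (7.6).

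**4. Illustration of size**

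Let f be the share of the Safety set outside the FAS, and d the mean exposure of that share.

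- Safety-set mean = (1 − f) × FAS mean + f × d
- Overstatement = FAS mean − Safety-set mean = f × (FAS mean − d)

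Assumptions not in the documents: FAS mean of 36 days, and d from 1 to 14 days (stopping before the D15 visit). For f, 10% is used as the upper bound, because the planned 10% covers all drop-out and non-evaluable patients, many of whom would remain in the FAS.

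| f | Safety-set mean, d = 1 | Safety-set mean, d = 14 | Overstatement (days) |
|---|---|---|---|
| 0% | 36 | 36 | 0 |
| 2% | 0.98×36 + 0.02×1 = 35.30 | 0.98×36 + 0.02×14 = 35.56 | 0.44 to 0.70 |
| 5% | 0.95×36 + 0.05×1 = 34.25 | 0.95×36 + 0.05×14 = 34.90 | 1.10 to 1.75 |
| 10% | 0.90×36 + 0.10×1 = 32.50 | 0.90×36 + 0.10×14 = 33.80 | 2.20 to 3.50 |

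**The case against.** **The omitted patients are those who could not tolerate the drops.** A reader might infer this, but the documents do not support it. Protocol 6.3.3 asks the investigator to make every effort to carry out the final-visit evaluations when a patient stops early, and SAP 5.1 allocates that visit to the next planned one. A single post-baseline performance assessment is enough for the FAS. Someone who stops for intolerance and attends therefore stays in the exposure table. Those left out are patients with no such assessment, whatever their reason for stopping.

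**The group may be empty.** This stands, and it is why the overstatement is conditional.

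**No planned result is biased.** This also stands. A reader might suppose that adverse event percentages are distorted. They are counts of patients over the Safety set, and no exposure-adjusted rate is planned.

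**The information is available elsewhere.** Partly so. SAP 7.2 tabulates device discontinuation with reasons on the Safety set and lists patients excluded from the FAS. SAP 7.1 plans by-patient compliance and exposure listings. A reader could trace these patients, but a listing is not a summary on the adverse event denominator.

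**A Safety-set table would mostly add missing values.** This may be true of some variables. Under SAP 5.2, days with instillation depend on the dates of Visits 2 and 3, and duration of exposure is missing if the day or month of the first or last instillation is missing. A phone compliance check could still supply those dates. The number missing should be shown.

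**The FAS and PP are what the protocol specifies.** The SAP keeps the protocol's label but not its effect, since the protocol FAS covered every dosed patient.

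**Conclusion.** The mismatch is clear in the current text: exposure and treatment summaries use a set that can be smaller than the adverse event population, and this arises only from the SAP's narrower FAS. Its consequence is conditional and modest. Mean exposure of the adverse event population could be overstated if any dosed patient lacks a post-baseline performance assessment. The illustrated range runs from nothing to about 3.5 days and rests wholly on the assumed 36-day mean, 1 to 14 days of use, and a share of up to 10%.

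The primary endpoint and the adverse event percentages are not affected. Medical history (SAP 7.5) is also confined to the FAS and PPS, and a reader might extend the point to it, but no harm from that is shown. This is a minor correction, worth making because it is cheap.

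**What to change.** - In SAP 7.6 and 7.7, add the Safety set to the listed populations, with the Safety set as the main display for exposure.
- In the exposure tables, report the number of patients whose exposure is missing.
- In SAP section 9, state that the narrower FAS no longer coincides with the Safety set, and that these tables have been extended for that reason.

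The cost is a few repeated tables, with some missing values for patients who have no post-baseline visit. No new data are needed. If the two sets turn out to be identical, the added tables simply repeat the FAS results.

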7.8 Performance Analyses

Primary and secondary performance endpoints will be primarily analysed on the FAS. Sensitivity analysis of the primary and secondary performance endpoints will be performed on the PPS.

7.8.1 Primary Performance Objective

The primary performance endpoint is the change from baseline (D1) to D36 in the CLDEQ-8 total score.

Descriptive statistics will be performed at each assessment time (baseline, D15 and D36) overall. Change from baseline will be described as well.

Main Analysis

To assess the performance of T2769, on change from baseline (D1) to D36 in the CLDEQ-8 total score, estimate of the change and associated 95% CI will be provided, as well as p-value for the paired t-test. Analysis will be performed on observed cased (without imputation).

The syntax with SAS using the UNIVARIATE procedure is detailed in Section 11.2.

Sensitivity Analyses

The analysis of the primary performance endpoint will be repeated on the PPS.

7.8.2 Secondary Efficacy Objectives

Secondary performance endpoints will be analysed based on observed cased (without imputation) on the FAS and the PPS.

CLDEQ-8 total score at D15

Change from baseline to D15 in the CLDEQ-8 total score will be analysed using the paired t-test in the same way as for the primary endpoint.

Soothing sensation at D15 and D36

CCI

OSDI total score at D15 and D36

CCI

CCI

CCI

[figure not shown]
Sponsor: Laboratoires Théa

Protocol: LT2769-003

Statistical Analysis Plan: V1.0 / 26-OCT-2023

[figure not shown]
Ocular discomfort score on the VAS at D15 and D36

CCI

[figure not shown]
Ocular symptom throughout the day at D15 and D36

CCI

[figure not shown]
Contact lens wearing time at D15 and D36

CCI

Conjunctival hyperaemia score at D15 and D36

CCI

CCI

Published date: 29Mar2023

Effective date: 12Apr2023

CONFIDENTIAL

Page 19 of 24

CCI

Sponsor: Laboratoires Théa

Protocol: LT2769-003

Statistical Analysis Plan: V1.0 / 26-OCT-2023

TBUT mean at D15 and D36

CCI

Total ocular surface staining grade at D15 and D36

CCI

Schirmer score (without anesthesia) at D15 and D36

CCI

Performance assessment by the investigator at D15 and D36

Assessment of the IMD performance assessed by investigator on a 4-point ordinal scale (Very satisfactory / Satisfactory / Not very satisfactory / Unsatisfactory) will be presented at D15 and D36 by frequency distribution for each modality.

7.9 Pharmacokinetic / Pharmacodynamic Analyses

Not Applicable.

7.10 Safety Analyses

All safety analyses will be performed using descriptive statistics overall using the Safety set, unless otherwise specified.

CCI

Published date: 29Mar2023

Effective date: 12Apr2023

CONFIDENTIAL

Page 20 of 24

7.10.1 Adverse Events

Ocular and systemic AEs reported during the investigation will be coded using MedDRA dictionary version 26.1, English or higher.

Summary tables will be performed on Treatment-Emergent AEs (TEAEs).

Ocular and systemic TEAEs will be analysed separately on the basis of the localisation and System Organ Class (SOC), unless stated otherwise.

The following definitions will be used:

- Treatment-emergent AEs: AEs that occurred after the first IMD instillation. AEs that occurred the day of the first IMD instillation or AE with an incomplete date that make it impossible to determine whether it is a TEAE or not will be reviewed during a data review meeting to decide if they have to be considered as TEAE or not,
- Related AEs: AEs suspected by the Investigator to have a relationship to IMD (as recorded on the AE eCRF page, Causal relationship to IMD = Causal relationship, Probable related, Possibly Related, or missing),
- Serious AEs: serious AEs (as recorded on the AE eCRF page, Is a serious AE? = Yes, or missing),
- AEs leading to premature IMD discontinuation: AEs leading to premature IMD discontinuation (as recorded on the AE eCRF page, Action taken with IMD = IMD withdrawn),

Summary of TEAEs

Separate summaries of ocular and systemic TEAEs will be performed presenting the number and percentages of patients experiencing at least one:

- TEAE,
- Serious TEAE,
- IMD-related TEAE,
- IMD-related serious TEAE,
- TEAE leading to premature IMD discontinuation.

Details of TEAEs

Separate descriptions of ocular and systemic TEAEs will be performed:

- Number and percentage of patients experiencing at least one TEAE as well as the number of TEAEs by SOC and PT. The same summary table will be performed for Serious TEAEs and TEAEs leading to premature IMD discontinuation.
- Number and percentage of patients experiencing at least one TEAE as well as the number of TEAEs by SOC, PT and relationship with IMD. The same summary table will be performed for Serious TEAEs.
- Number and percentage of patients experiencing at least one TEAE as well as the number of TEAEs by SOC, PT and severity.

Three additional tables will be produced:

- Number and percentage of patients experiencing at least one non-serious TEAEs (ocular or systemic together), as well as the number of these TEAEs by SOC and PT
- Number and percentage of patients experiencing at least one non-serious TEAEs (ocular or systemic together) when percentages by PT is $\geq 5\%$, as well as the number of these TEAEs by SOC and PT
- Number and percentage of patients experiencing at least one SAE (ocular or systemic together), as well as the number of these SAEs by SOC and PT

Individual listings of AEs

Listings of AEs (ocular and systemic separately) will be produced:

- for non-emergent AEs on enrolled patients,
- for TEAEs, serious TEAEs and TEAEs leading to premature IMD discontinuation.

The following variables will be presented:

- Patient number,
- Studied eye (right eye / left eye),
- Gender,
- Age at baseline (Day 1),
- Diagnosis (verbatim),
- SOC,
- PT,
- Localisation (right eye / left eye / both eyes),
- Date of onset,
- Time to occurrence (days) from the date of the first IMD instillation,
- Date of recovery / date of death, if any,
- Duration (days),
- Outcome,
- Details of AEs,
- Frequency and details (i.e. Did the AE appear upon IMD administration; If yes, mean duration of each episode),
- Severity,
- Seriousness,
- Relationship to IMD,
- Relationship to protocol procedure,
- Action taken with IMD,

- Required treatment,
- Required surgical/medical procedure.

Listings will be sorted by patient identifier and date of onset.

Listing of Deaths, Other Serious Adverse Events, Discontinuations due to AEs and Other AEs of Special Interest (if applicable) will be also provided for narratives (in word and excel files).

Discontinuations due to AEs include IMD-related AE leading to premature IMD discontinuation OR study withdrawal (*i.e.*, drug related AE with action taken = drug withdrawn OR End of study with premature discontinuation due to this AE).

